Submission Date/version: 3rd March, 2018/Version 1

Study Title: Efficacy of preoperative intravenous iron isomaltoside in colorectal cancer surgical patients with iron deficiency anaemia compared to standard care: a pilot randomized controlled trial

Principal Investigator: [name] [name] (1)

Co-investigators: [name] [name] (2), [name] [name] (1), [name] [name] (3), [name] [name] (3)

(1) Department of Anaesthesia and Intensive Care, Prince of Wales Hospital, Hong Kong

(2) Department of Anaesthesia and Intensive Care, The Chinese University of Hong Kong

(3) Division of colorectal surgery, Department of Surgery, The Chinese University of Hong Kong

Area of Research: Perioperative medicine - patient blood management

Abstract: Iron deficiency anaemia is a common condition among colorectal surgical patient. Untreated anaemia would lead to increase in blood transfusion, surgical complications and mortality. Treatment with oral iron sulphate is poorly tolerated due to side effects. Intravenous iron supplement provides an alternative way to rapidly replace iron deficit during the preoperative period among surgical patients. Evidence is growing for its effect in rising hemoglobin level and reducing blood transfusion, at the same time supporting its safety profile.

We plan for a single-centered, randomized controlled trial to examine the effect of intravenous iron compared to standard care in terms of hemoglobin level/serum ferritin increment, need for blood transfusion, duration of hospital stay, quality of recovery and surgical complication rate, as well as safety profile among colorectal cancer surgical patients in Hong Kong. We propose the following pilot RCT for exploring the effect size and study process in conducting the above-mentioned large-scale RCT.

1. Background

Iron deficiency is the most common nutritional deficiency in the world, with approximately two billion people worldwide suffering from the condition according to World Health Organization data in 2001.¹

The human body contains about 3500mg of iron (50mg/kg body weight); two-thirds of which exists as part of hemoglobin, 10% are stored in myoglobin and various enzymes involved in cellular respiration, while the remaining 20% are stored as ferritin and haemosiderin inside liver, bone marrow and macrophages in the reticuloendothelial system.^{2,3} Ferritin is a predominantly intracellular protein that stores iron and releases it in a controlled fashion. It acts as a buffer against iron overload and iron deficiency in humans. Small amounts of ferritin are also secreted into the plasma acting as iron carriers. The serum ferritin level is positively correlated with the total body iron store. A low serum ferritin level is thus a useful marker of reflecting iron deficiency.

One-third of patients undergoing non-cardiac surgery suffers from anaemia, of which iron deficiency or sequestration were the main contributors (75%).⁴ Among this population, the colorectal surgical patients are especially prone to iron deficiency due to an increased iron loss from tumour bleeding, and a reduced iron intake due to poor dietary intake or gastro-intestinal malabsorption. Erythropoiesis is disrupted as a result, leading to iron deficiency anaemia, typically manifested with microcytic hypochromic red cells and low serum ferritin level.

Oxygen carrying capacity in blood is decreased in anaemic patients, which leads to decreased oxygen delivery to tissues. This may have detrimental effects on surgical outcomes. Anaemic patients are more prone to develop cardiac event, and it is associated with an increased risk of 30-day mortality.⁵ Although allogenic blood transfusion can readily correct perioperative anaemia, it was associated with an increased risk of cancer-related mortality (OR 1.71, 95% CI: 1.43-2.05), postoperative infections (OR 3.27, 95% CI: 2.05-5.20), surgical re-intervention (OR 4.08, 95% CI: 2.18-7.62), and all-cause mortality (OR 1.72, 95% CI: 1.55-1.91) in a systematic review of 20,795 colorectal cancer patients.⁶ Thus, preoperative optimization of anaemia is a

key concept in the patient blood management strategy to minimize perioperative blood transfusions and its related complications.

Timely correction of preoperative iron deficiency is a possible intervention with the aim to boost up haemoglobin level before surgery. The conventional management of iron deficiency is oral iron supplementation. However, oral ferrous sulphate is often not well tolerated by patients due to its gastrointestinal side effects including constipation and dyspepsia. Thus iron replacement via oral route is often ineffective due to low adherence, and variable absorption. Moreover, replacement via the oral route is slow and may not be adequate to replace iron deficit within short time frame of intervention before operation.

Intravenous iron therapy is an alternative, which allows more efficient iron replacement as a higher dose of iron can be administered as a single dose, and bypasses gastrointestinal absorption. Free iron could not be given via intravenous route, as it would lead to acute toxicity. Therefore, parenteral formulae contain iron molecules embedded in carbohydrate matrix structure, which allows iron to be released in a gradual manner. Iron isomaltoside 1000(Monofer®) is an unbranched oligosaccharide with mean molecular weight of 1,000Da, with iron strongly bound within the molecules. Compared to other formulae in which the iron are more loosely bound, iron isomaltoside potentially causes less oxidative stress and toxicity, allowing higher dose to be given over a short period of time. For example, iron isomaltoside can be given at a dose of 20mg/kg body weight, which is higher than that of ferric carboxymaltose, which is 15mg/kg body weight.⁷ Most published studies of perioperative use of intravenous iron therapy showed a positive effect in increasing the hemoglobin level and reducing the number of blood transfusions.⁸

Among colorectal cancer patients, several randomized controlled trials and cohort studies showed favourable results supporting the use of preoperative intravenous iron therapy. Keeler et al.'s conducted a RCT (n=116) showing a higher haemoglobin rise in IV iron group (1.55g/dL, IQR 0.93-2.58) than the oral iron group (0.5g/dL, IQR -0.13-1.33) among colorectal cancer surgical patients.⁹ A prospective, multicenter,

observational study (n=266) in patients undergoing elective colon cancer surgery showed a significant reduction in transfusion rates (9.9% vs 38.7%) and length of stay (8.4 vs 10.9 days) in the IV ferric carboxymaltose group compared to oral iron.¹⁰ A recent retrospective analysis published by Laso-Morales et al in 2017¹¹ showed that anaemic colorectal cancer patients who received IV iron were able to achieve similar haemoglobin level as non-anaemic patients on day of surgery and remained similar at postoperative day 30.

In Hong Kong, there has been a rising trend in the number of patients diagnosed with colorectal cancer over the past decade. The number of colorectal cancer new case per year has risen from 3,706 in 2005 to 5,036 in 2015, such that colorectal cancer is now the top cancer in Hong Kong.¹² At Prince of Wales Hospital, the majority of elective resection surgeries for colorectal cancer are performed with minimally invasive approach, including laparoscopic surgery or robotic assisted laparoscopic surgery. Due to technological advances in surgical instruments, the laparoscopic approach has become the new standard of care instead of the open approach even for low-lying tumours. Blood loss is much reduced and blood transfusion rate is much lower compared to the value quoted in most studies published overseas (>30%). Early recovery after surgery (ERAS) is implemented in most cases, such that the length of hospital stay is short. The above characteristics makes the currently published evidence, which has a higher baseline blood transfusion rate, longer length of stay, and a higher rate of open surgeries, less applicable to our patient population.

2. Study Objectives

This pilot study aims to explore the feasibility of conducting a large scale randomized controlled trial to determine the efficacy and safety of intravenous iron isomaltoside(Monofer®) therapy for the colorectal cancer surgical patients with iron deficiency anaemia compared to standard care.

As discussed above, the patient population in Prince of Wales Hospital is characterized by a majority of laparoscopic surgery with low blood loss and transfusion rate, as well as short hospital stay at baseline. A smaller effect size in terms of reduction in

transfusion rate and hospital stay is thus expected, which implies that a large sample size would be required to conduct a RCT with adequate statistical power. Before embarking on such a large-scale research project, it is necessary to conduct a feasibility trial to estimate recruitment rate, sample size and allow proper logistics management.

There are two areas to be assessed in this pilot trial including study process and the predicted effect size.

2.1. Study process:

The number of patients diagnosed with colorectal cancer listed for elective resection per month will be studied, and the prevalence of iron deficiency anaemia among these patients will be recorded. All of the eligible patients satisfying the recruitment criteria stated below would be invited to join the pilot study, and the refusal rate will be noted. The information is required to calculate the recruitment rate of the study. The median waiting time for surgery will also be calculated. We envision that a recruitment rate of more than 60%, 5 patients per month and a median waiting time of 4 weeks will be necessary for conducting a larger RCT.

2.2. Effect size:

In this pilot trial, we plan to explore the effect size of the primary outcomes for the proposed RCT, including haemoglobin rise and serum ferritin rise associated with the intravenous iron treatment group compared to standard care. The secondary outcomes to be measured will include perioperative blood transfusion rate, hospital length of stay, quality of recovery scores, surgical complications, adverse reactions and days (alive and) at home within 30 days of surgery (DAH₃₀). As stated before, the baseline transfusion rate for elective colorectal surgeries in our population is lower compared to international studies, therefore it would be inaccurate to use existing data to estimate the sample size.

[figure not shown]
3. Study Design

3.1. Methodology

A single-centered, superiority, 2-arm, randomized controlled trial is planned to

determine the efficacy and safety of preoperative intravenous iron isomaltoside (Monofer®) therapy compared to standard care (control) in colorectal cancer patients undergoing elective tumour resection surgery. The study design is outlined in the diagram in Figure 1.

Figure 1. Overview of study design

For the pilot study to assess the feasibility of conducting the actual large-scale trial, 40 patients (20 in the treatment arm and 20 in the control arm) will be recruited. The study design of the pilot study would be identical to the above-proposed trial with the aim to explore the study process and the predicted effect size.

3.2. Study population

Consecutive patients diagnosed with colorectal cancer listed for elective curative tumour resection surgery (including open and laparoscopic approach) will be screened for eligibility based on the criteria listed below. Baseline blood tests (including: complete blood counts, renal and liver function, iron profile (serum ferritin, transferrin saturation/TSAT), serum B12 and folate) will be collected as a routine preoperative workup.

3.3. Inclusion criteria (All criteria must be fulfilled)

- Age >18 years old with written informed consent
- Anaemia defined as: hemoglobin concentration < 13g/dL (same cut-off for both male and female patients according to the International consensus statement on the perioperative management of anaemia and iron deficiency)²
- Laboratory test confirmed iron deficiency: serum ferritin <30mcg/L alone *or* serum ferritin 30-100mcg/L with TSAT < 20%

3.4. Exclusion criteria (None of the criteria must be fulfilled)

- Pregnancy or lactation
- Other known causes of anaemia apart from iron deficiency: untreated B12/folate deficiency, hemolytic disease, hemoglobinopathy/thalassemia, chronic renal failure on dialysis
- Presence of iron overload (serum ferritin > 300g/dL or TSAT > 50%); known hemochromatosis
- Previous or ongoing iron replacement/use of erythropoietin within 12 weeks before recruitment
- Known hypersensitivity towards iron isomaltoside
- Significant liver function derangement (AST/ALP exceeding three times upper

limit of normal range)

- Use of preoperative immunosuppressant therapy
- Participation in another ongoing interventional clinical trial(s)
- Patients with less than 3 weeks waiting time to surgery

3.5. Consent

Eligible subjects will be recruited as early as possible when all the above criteria have been fulfilled. They will be approached by research personnel for obtaining written informed consent. Information sheet with detailed explanation of the objectives, duration, data collections, intervention involved and safety issues will be provided for the recruited patients. They will be provided with contact information of the research team such that they can ask questions, or withdraw from the trial if needed.

3.6. Definition of primary and secondary outcomes:

3.6.1. Effect size

Primary Outcomes:

- Preoperative change in hemoglobin concentration (g/dL) and change in serum ferritin (mcg/L), which is, the difference between the value at diagnosis and preoperative day.

Secondary Outcomes:

- Units of red blood cells transfused in perioperative period in the two groups, defined as:
 1. Preoperative - from randomization to operation;
 2. Intraoperative – inside operating theatre and recovery room;
 3. Postoperative - from arrival to ward after operation to discharge.
- Duration of hospital stay (days).
- Quality of recovery as measured by questionnaire (QoR-15(Chinese)) completed on postoperative period. The QoR-15 (See Appendix A) includes the items measuring pain, physical comfort, physical independence, psychological support and emotional state.¹³ The QoR-15 score ranges from 0 to 150 and takes about 3 minutes to complete.¹³ The validity (convergent, construct, discriminant), reliability (internal consistency, split-half, test-retest), responsiveness,

acceptability and feasibility properties have been well established.¹³

- Incidence of adverse reactions/serious adverse events to intravenous iron administration and adverse reaction to blood transfusions (Adverse reactions: any unintended responses related to drug/blood products administrations e.g. skin rash, pain, neurological/respiratory/cardiovascular symptoms. Serious adverse events: life-threatening/require additional period of hospitalization/results in disability/mortality eg. Anaphylaxis, acute hemolytic transfusion reactions, organ failure etc.).
- Rate of surgical complications recorded and graded according to Clavien Classification of Surgical Complications.¹⁴ (See Appendix B)
- Days (alive and) at home within 30 days of surgery (DAH₃₀)
 - A parameter incorporating the duration of initial hospital stay associated with the index surgery, re-hospitalization due to post-discharge complications, discharge to institutional care and early deaths within 30 days post operatively. It has been validated as an effective patient-centered outcome measure for perioperative trials.¹⁵
 - Method of calculation – refer to Appendix C

3.6.2. Study process:

- Patient recruitment rate (number of recruited patient/total number of eligible patients x 100%)
- Number of patients recruited per month.
- Median waiting time to surgery (days).

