3.8. Baseline patient demographics and clinical data collection

After patient recruitment, baseline characteristics including age, sex, body weight and height, ASA grading, important past health comorbidities (hypertension, diabetes mellitus, significant cardiovascular diseases, known hemolytic conditions/hemoglobinopathy), medication history will be collected. The information regarding baseline hematological profile (hemoglobin level, ferritin level) at the time of recruitment will be recorded.

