3.9. Standard perioperative care apart from the study interventions

Standard anaesthetic preoperative assessment will be carried out either in the preoperative assessment clinic or by the list anaesthetist on the day before surgery, according to the routine practice in our hospital for all elective colorectal cases. Patients are allowed to continue their usual medications as directed by the parent surgical team and case anaesthetists. Upon recruitment, patients will not receive iron supplements other than intravenous iron isomaltoside.

Following the existing practice, patients for elective colorectal cancer resection operations are admitted to surgical wards one day before the operation. The second batch of study blood tests (including complete blood count, iron profile) will be taken along with cross match on admission. Bowel preparation will be undertaken if deemed necessary by the parent team.

General anaesthesia will be provided by anaesthetists blinded to the study allocation, without restrictions on the anaesthetic agents and analgesic modalities to be used. As per usual practice within the department, intravenous induction will be achieved with propofol and fentanyl, followed by maintenance with sevoflurane/desflurane. Muscle relaxation with non-depolarizing muscle relaxant (atracurium/cisatracurium/rocuronium) will be maintained throughout the operation, followed by reversal with neostigmine/atropine at the end of operation. Analgesia will be achieved by multimodal approach, by a combination short and long acting opioids (fentanyl/morphine), tramadol, paracetamol, non-steroidal anti-inflammatory drugs (NSAIDs) and local anaesthetics (intravenous infusion and/or local infiltration) at the discretion of the list anaesthetists. Antiemetics will be given as routine either with ondansetron, dexamethasone or metoclopramide.

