3.12. Follow up/assessment

Data on the primary and secondary outcomes as listed above would be collected. Investigators will access the patients' records via the Hospital Authority computer system and the hardcopy documents in the wards. Data on the hematological profile throughout study period (on diagnosis, preoperative day, post-operation day one, on discharge) will be retrieved from the computer records. The number of red cell transfusion will be retrieved from the computer records as well as counterchecking with

anaesthetic records/progress notes. The length of hospital stay (for the operation and DAH₃₀) will be counted by referring to computer patient records.

The quality of recovery is assessed by a self-reported quality of recovery questionnaire (QoR-15)¹³, which assess different dimensions of recovery including pain, physical comfort, physical independence and mental well-being.

4. Statistical analysis

Missing data will be checked and imputed to preserve power. The Shapiro-Wilk test will be used to check data for normality. Generalized estimating equations will be used to examine the changes in haemoglobin level and serum ferritin levels over time. Expected skewed data, such as the quality of recovery score, the number of days of hospital stay, units of transfusion and DAH₃₀, will be reported as median and interquartile range, and compared between treatment arms by Mann-Whitney U tests. Two-tailed χ^2 test will be used to analyze categorical data between groups. All of the analysis would be intention-to-treat and with a statistical significance level defined at $P < 0.05$.

5. Expected impact on study/patient care

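### The primary haemoglobin and ferritin changes start from an undefined diagnosis value that is tied neither to the recruitment baseline nor to randomisation

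*Combined protocol and SAP*

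**What the plan says.** - **Primary outcome (3.6.1).** The change in haemoglobin and in ferritin is "the difference between the value at diagnosis and preoperative day".
- **Follow-up (3.12).** The haematology time points are "on diagnosis, preoperative day, post-operation day one, on discharge) will be retrieved from the computer records". Neither recruitment nor randomisation is listed.
- **Baseline data (3.8).** The "baseline hematological profile (hemoglobin level, ferritin level) at the time of recruitment will be recorded".
- **Source of the samples (3.2, 3.9).** Baseline bloods, including the iron profile, "will be collected as a routine preoperative workup". Later, "The second batch of study blood tests (including complete blood count, iron profile) will be taken along with cross match on admission".
- **Timing of recruitment (3.5).** "Eligible subjects will be recruited as early as possible when all the above criteria have been fulfilled". No maximum interval is given.
- **Transfusion (3.6.1, 3.4).** The first transfusion window is "Preoperative - from randomization to operation". The exclusions name iron and erythropoietin use in the 12 weeks leading up to recruitment, but not transfusion.
- **Analysis (4).** Haemoglobin and ferritin over time are analysed by generalized estimating equations (GEE). No baseline time point or baseline covariate is specified.
- **Use of the result (5).** The effect size on the primary outcomes is to help set the sample size of the larger trial.

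**The concern.** The outcome sections and the baseline section name different start points, and neither is tied to randomisation. If the diagnosis value is older than the recruitment value, the primary change contains a segment that ended before anyone was allocated. Section 1 names tumour bleeding as a source of iron loss in these patients, so haemoglobin could fall in that segment. A transfusion in the same segment would raise it, yet would appear in no transfusion outcome. Neither movement can be an effect of treatment.

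At stake are the interpretation of the change within each arm, the precision of the between-arm comparison, and the SD carried forward to plan the larger trial.

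**Working it through.** The plan gives no power, SD or effect size for its 40 patients, so there is no stated figure to reproduce. The check is first textual; arithmetic is added only for scale.

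**1. Are the two start points the same sample?**
- *For one sample.* Section 3.2 takes baseline bloods at routine workup. Those results establish eligibility under 3.3, and so identify the iron deficiency anaemia. Recruitment follows promptly (3.5). Section 3.9 calls the admission sample the second batch, which implies one earlier batch. Section 3.8 says values are recorded, not that blood is drawn again.
- *For two samples.* Section 3.2 applies the word diagnosed to the cancer, and patients already so diagnosed are then screened. Read literally, diagnosis precedes the screening bloods. The iron profile is described only as part of that workup, so on this reading some patients might have no ferritin at diagnosis, and section 4 would impute it.
- *Result.* One screening sample is the likelier intent, but no section states it. Even then, the time from sample to randomisation has no limit.

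**2. What would an earlier value do?** Write D for the diagnosis value, R for the value at randomisation and P for the preoperative value. Then P - D = (P - R) + (R - D). The segment R - D precedes allocation, so its expected value is the same in both arms and cancels from the between-arm difference.

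Its effect on variance is Var(P - D) = Var(P - R) + Var(R - D) + 2 Cov(P - R, R - D). R enters the two segments with opposite signs. If R - D were only measurement error or short-term fluctuation of constant variance v, then Var(R - D) = 2v and the covariance is -v, so the added variance is 2v - 2v = 0. Variance rises by the full drift variance only if drift is independent of later change.

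**3. Illustrative variance inflation.** The trial of intravenous versus oral iron cited in section 1 reports an IQR of 0.93-2.58 g/dL in its intravenous arm. SD = (2.58 - 0.93)/1.349 = 1.22, taken as 1.2. Assume an independent drift SD d:
- d = 0.5: (1.44 + 0.25)/1.44 = 1.17, and 40/1.17 is about 34 patients' worth of information.
- d = 0.7: (1.44 + 0.49)/1.44 = 1.34, and 40/1.34 is about 30.
- Same sample, d = 0: ratio 1, no loss.

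**4. Illustrative power.** The oral arm's SD is (1.33 + 0.13)/1.349 = 1.08; pooled with 1.22 this gives 1.155. The difference in medians is 1.55 - 0.50 = 1.05 g/dL. Total SD = √(1.155² + d²); SE = SD × √(2/20); power ≈ Φ(1.05/SE - 1.96); n per arm for 80% power = 2(1.96 + 0.84)² SD²/1.05².

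| Assumed d (g/dL) | Total SD | SE of difference | Power, 20 per arm | n per arm for 80% | SE of chance imbalance, d√(2/20) |
|---|---|---|---|---|---|
| 0 | 1.155 | 0.365 | 82% | 19 | 0 |
| 0.5 | 1.258 | 0.398 | 75% | 23 | 0.16 |
| 1.0 | 1.528 | 0.483 | 58% | 34 | 0.32 |

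**5. Check on bias.** In 40,000 simulated trials per setting, with 20 per arm, a mean pre-randomisation change of +0.5 or -0.5 g/dL moved the treatment-arm change from about 1.05 to about 1.55 or 0.55, and the control-arm change from 0 to about +0.50 or -0.50. The between-arm difference stayed at about 1.05.

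**The case against.** The strongest reply is that there is one pre-treatment sample, called diagnosis in 3.6.1 and 3.12 and baseline in 3.8, so no number would change. Sections 3.2, 3.3, 3.5 and 3.9 make this the likelier intent. It is still an inference, because diagnosis is undefined and the interval to randomisation is open.

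Other objections also carry weight:
- Only 3.6.1 defines the change, and 3.12 agrees with it; 3.8 defines no outcome. So the protocol does not give two rival definitions of the primary outcome. What remains is doubt about which value the word diagnosis points to.
- The drift SD has no source in the documents, and independence is an assumption. The reference SD comes from a trial whose own baseline is not described here and which may already include such drift.
- Section 3.1 gives the pilot and the larger trial the same design. If the larger trial keeps the same start point, the pilot SD is the right planning SD for it. The avoidable cost is then a larger trial than a better start point might need.
- Section 1 describes a low local transfusion rate, and nothing suggests that transfusion before randomisation is common. Starting the transfusion outcome at randomisation is itself correct.

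A reader might infer that pre-randomisation change contaminates the estimated treatment effect. The documents do not support that: allocation is random and comes after the change, so the between-arm difference is unbiased in expectation.

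**Conclusion.** The point holds as an undefined start to the primary change, with no stated link to randomisation. The consequences are conditional on an earlier value being used: within-arm changes shift by the mean drift, and variance and chance imbalance can rise with 20 per arm.

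The size cannot be derived from the documents. It is zero if the samples coincide, and could be near zero if drift is mostly short-term fluctuation. It is about 17-34% extra variance only with an assumed independent drift SD of 0.5-0.7 g/dL. A reader might take that as an established loss of 6 to 10 patients' information; it is an illustration. Nor do the documents show that two different samples exist.

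The change is still worth making. It removes the ambiguity, fixes a start point next to allocation, and supplies the baseline adjustment that section 4 leaves unspecified.

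**What to change.** - In 3.6.1, 3.8, 3.12 and section 4, define baseline as the last available haemoglobin and ferritin before randomisation. If the screening sample in 3.2 is the only one, say that it is the baseline.
- Record the date of that sample and the interval to randomisation, and report the interval by arm.
- Compute the primary change from this baseline.
- In section 4, adjust for it as a covariate in the primary GEE analysis of haemoglobin and of ferritin, and state that baseline is then not also modelled as a response.

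The cost is protocol and SAP wording and one recorded date per patient (two if the haemoglobin and ferritin samples differ). No new blood draw is required, because the value is already collected. If only the screening sample exists, the computed change is unaltered and the gain is clarity plus the adjustment.
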